PART B STUDY DESCRIPTION

TITLE OF PROTOCOL	Mechanisms of Weight Loss with SGLT2 Inhibition			
Principal Investigator	[name]			
Co-Investigators				
Mailing Address	[name]			
E-Mail Address	[contact]			
	[name]			
P.I.'s Telephone	[name]	P.I.'s Pager [name]	[contact]	
Sponsor/Funding Source	Janssen Sc	ientific Affairs, LLC		

B1. PURPOSE OF PROTOCOL

The primary purpose of this study is to examine change in body weight in individuals with type 2 diabetes and overweight or obesity treated with the SGLT2 inhibitor canagliflozin compared to placebo. Secondary objectives include investigation of changes in resting energy expenditure, body composition, glycemia, metabolic markers, and food intake with SGLT2 inhibition.

B2. SIGNIFICANCE AND BACKGROUND FOR THE STUDY

Canagliflozin is a sodium-glucose transporter subtype 2 (SGLT2) inhibitor that was approved by the FDA for the treatment of Type 2 diabetes in March, 2013. Canagliflozin, at the doses of 100mg and 300mg daily, improves blood sugar control by a novel mechanism which causes the kidneys to block reabsorption of about 50-80 grams of glucose. Canagliflozin lowers the renal threshold for glycosuria and causes excess glucose to be excreted in the urine.

Canagliflozin is also associated with a 3-5% reduction in body weight among obese individuals with type 2 diabetes. Weight loss appears to be most rapid during the first 18 weeks of treatment and sustained over 104 weeks of treatment. The mechanisms of weight loss with canagliflozin are not completely understood. The increased energy expenditure associated with glycosuria is typically 300-400 kcal/day, however the magnitude and duration of this energy loss has not been carefully studied. Specifically, it is not known whether canagliflozin changes resting metabolic rate (RMR), and there are few published data on the change in body composition associated with canagliflozin therapy. Careful investigation of the magnitude and duration of changes in energy expenditure during canagliflozin treatment is clinically relevant as it may inform recommendations about lifestyle modification, including a reduced calorie diet and physical activity.

References

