If the defect is combined with a serious adverse event, the study-site personnel must report the PQC to Janssen Scientific Affairs, LLC according to the serious adverse event reporting timelines. A sample of the suspected product should be maintained for further investigation if requested by Janssen Scientific Affairs, LLC.

B. Statistical Considerations

Sample Size Justification: There are no published data on change in resting metabolic rate with canagliflozin treatment. We therefore calculated sample size based on change in body weight, our primary outcome. Published data show approximately 3kg placebo-corrected weight loss after 12 weeks of treatment with canagliflozin compared to placebo in individuals with type 2 diabetes and obesity (Stenlof et al, 2013). Based on a 3 kg difference in body weight between canagliflozin and placebo and a SD of 3.3, the probability that this study will detect a treatment difference at a two-sided 0.05 significance level is 80% if we have 42 study completers. We plan to screen 60 subjects in order to enroll approximately 50 subjects (8-10 screen failures) and obtain 42 study completers (approximately 8-10 dropouts). Data from subjects who complete at least 12 weeks of treatment will be used in the final analysis.

Data analysis: Descriptive statistics with 95% confidence intervals will be used to describe baseline characteristics of the study population. The primary endpoints of change in body weight and BMI will be analyzed using an analysis of covariance (ANCOVA) model. We will use repeated measures analysis of variance to assess changes in body weight and resting metabolic rate at each study visit/timepoint. We will also analyze change in body composition between baseline and end of study. Treatment group will be the fixed effect and corresponding baseline values at the start of each treatment period will be the covariates. We will stratify based on baseline BMI, glycemic control (A1C), and diabetes treatment (lifestyle vs pharmacologic treatment at baseline). The least squares mean differences between treatments (canagliflozin vs placebo) and the associated 95% confidence intervals will be estimated based on this model.

Secondary endpoints will be analyzed using an ANCOVA model as above. The least squares mean differences between treatments and the associated 95% confidence intervals will be estimated based on this model.

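### The by-visit analysis of weight and RMR is specified only as repeated measures ANOVA; depending on how it is run, weight intervals may be miscalibrated or incomplete subjects lost, and an MMRM should replace it

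*Combined protocol and SAP*

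**What the plan says.** All of this is in the combined protocol and SAP, section B3.B (Statistical Considerations), unless stated otherwise.

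- **Primary analysis:** "The primary endpoints of change in body weight and BMI will be analyzed using an analysis of covariance (ANCOVA) model".
- **By-visit analysis:** "We will use repeated measures analysis of variance to assess changes in body weight and resting metabolic rate at each study visit/timepoint".
- **Model terms:** "Treatment group will be the fixed effect and corresponding baseline values at the start of each treatment period will be the covariates". Stratification by baseline BMI, A1C and diabetes treatment is added. Visit and treatment-by-visit are not listed.
- **Intervals:** least squares mean differences are to be reported, and "the associated 95% confidence intervals will be estimated based on this model". This follows both the ANCOVA and the repeated measures sentences, so which model is meant is unclear.
- **Who is analysed:** the sample size paragraph says "Data from subjects who complete at least 12 weeks of treatment will be used in the final analysis". The last paragraph of the same section excludes only those who leave before week 8. The two rules differ, and both admit subjects with no week-18 value.
- **Visits (B3.A):** week 0, then weeks 2, 4, 8, 12 and 18, so five post-baseline visits.

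The section states no covariance structure, sphericity correction, degrees-of-freedom method or rule for missed visits. Section B2 gives the reason for following the time course: "Careful investigation of the magnitude and duration of changes in energy expenditure during canagliflozin treatment is clinically relevant".

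**The concern.** Repeated measures ANOVA is most often run in one of two ways, and each carries its own risk here.

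- **Univariate form with pooled error.** The treatment difference at every visit gets the same standard error, which is right only if the variance is the same at every visit. Change from baseline is zero for everyone at week 0, and B2 describes weight loss as fastest over the first 18 weeks, which is the whole trial window. A spread that widens over time is therefore plausible for weight. If it does widen, late intervals are too narrow and early ones too wide.
- **Wide (multivariate) form.** Each subject needs a complete row. One missed interim visit, or no week-18 value, removes the whole subject, although the inclusion rules admit subjects without week 18.

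In addition, the listed terms, taken literally, give one average treatment difference and not one per visit.

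At stake is the reliability of the weight time course and, for RMR, the only by-visit analysis planned.

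**Working it through.** **1. The plan's own figure.** Inputs: "Based on a 3 kg difference in body weight between canagliflozin and placebo and a SD of 3.3"; and the power to "detect a treatment difference at a two-sided 0.05 significance level is 80% if we have 42 study completers"; allocation 1:1 (B3.A), so 21 per arm.

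Noncentrality = 3 / (3.3 × √(2/21)) = 3 / 1.018 = 2.95, with 40 degrees of freedom. The exact noncentral-t power is 82.0%. With 20 per arm it is 80.0%. The stated 80% is reproduced.

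**2. Pooled error.** With k = 5 visits, the error variance for a group difference at one visit in a split-plot ANOVA is

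[MS_between + (k − 1) × MS_within] / k,

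which equals the plain average of the five visit variances. Correlation between visits affects only the degrees of freedom, so it matters little. For large samples, coverage at visit j is

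2Φ(1.96 × SD_pooled / SD_j) − 1.

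The documents give one SD (3.3 kg) and tie it to no visit. The profiles below are assumptions, all ending at 3.3 kg at week 18.

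| SD at weeks 2, 4, 8, 12, 18 (kg) | Pooled SD | Miss rate, week 2 | Miss rate, week 18 |
|---|---|---|---|
| 3.3 throughout | 3.30 | 5.0% | 5.0% |
| 2.3, 2.5, 2.8, 3.0, 3.3 | 2.80 | 1.7% | 9.6% |
| 1.4, 1.8, 2.4, 2.8, 3.3 | 2.44 | 0.1% | 14.8% |
| 1.1, 1.56, 2.2, 2.69, 3.3 (proportional to √week) | 2.31 | about 0% | 17.1% |

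Worked for the second row: (5.29 + 6.25 + 7.84 + 9.00 + 10.89) / 5 = 7.854; √7.854 = 2.80; 2.80 / 3.3 = 0.85; coverage 2Φ(1.664) − 1 = 90.4%.

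Simulation with 21 per arm, Satterthwaite degrees of freedom, an assumed AR(1) correlation of 0.85 and 4,000 trials per profile gave week-18 miss rates of 5.0%, 9.8%, 15.2% and 17.6%, in the order of the table. A second simulation, 5,000 trials per profile with week-2 SDs from 1.1 to 2.4 kg, gave 8.7% to 16.8%, and 4.5% with a constant SD. The two differ in the √week profile (17.6% and 16.8%) by no more than simulation error. Visit-specific variances held the miss rate near 5% in both.

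Mean interval widths from the first simulation, for the three growing profiles:

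| Profile (week-2 SD) | Pooled, every visit | Visit-specific, week 2 | Visit-specific, week 18 |
|---|---|---|---|
| 2.3 kg | 3.44 kg | 2.85 kg | 4.10 kg |
| 1.4 kg | 2.98 kg | 1.73 kg | 4.09 kg |
| 1.1 kg | 2.83 kg | 1.37 kg | 4.08 kg |

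The pooled interval is thus 16% to 31% too narrow at week 18 (1 − 3.44/4.10; 1 − 2.83/4.08) and 20% to 107% too wide at week 2 (unrounded widths 3.436/2.852 and 2.825/1.367).

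**3. Row deletion.** The documents give no missed-visit rate. If each of the four interim visits is missed independently with probability q, the completers with a full row number 42 × (1 − q)⁴:

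- q = 3%: 42 × 0.885 = 37.2
- q = 5%: 42 × 0.815 = 34.2
- q = 10%: 42 × 0.656 = 27.6

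Any admitted subject without week 18 is also deleted. The plan expects 8 to 10 dropouts among about 50 enrolled. How many of these fall in this group depends on when they leave and which inclusion rule applies.

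**The case against.** The strongest reply is that the plan does not call its method classical or univariate. Its wording, with a fixed effect and least squares means, also fits a likelihood-based repeated measures model that has visit-specific variances and keeps partial data. The sentence listing the terms can be read as describing the ANCOVA, with visit implied as the within-subject factor. This stands to the extent that neither fault can be called a settled feature of the plan. It does not remove the point, because the text does not exclude the implementations that fail.

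A reader might also infer four stronger things that the documents do not support:

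- **That both faults will occur together.** A wide-format analysis can use visit-specific errors, and a long-format univariate analysis can keep incomplete subjects.
- **That the trial's power falls.** The two-sample calculation in step 1, repeated with 37, 34 or 28 subjects, gives about 77%, 73% or 64%. That is not the primary test. Weight is assigned to ANCOVA, which does not need the interim visits, so a completer who misses week 4 stays in.
- **That the week-18 weight interval is certainly too narrow.** This needs an SD that grows over time, which is plausible but not documented. On the natural reading, the primary weight interval comes from the ANCOVA and carries no pooled error, although the plan's reference to its model is ambiguous.
- **That RMR intervals are miscalibrated.** The passage in B2 on magnitude and duration concerns energy expenditure, but the documents give no variance for RMR change and every calculation here is for weight.

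**Conclusion.** The concern holds in conditional form. The by-visit analysis is under-specified, and two common ways of running it would do harm. With pooled error and an SD of weight change growing to 3.3 kg at week 18, the nominal 95% by-visit weight interval misses about 9% to 17% of the time at week 18 and 0% to 2% at week 2. With wide-format data, the assumed missed-visit rates leave about 37, 34 or 28 of 42 completers in this analysis, and admitted subjects without week 18 are lost as well.

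The SD profile, the correlation and the missed-visit rates are all assumptions. The direction of the first result depends on the SD growing. The consequence is confined to the time-course results. It is still worth acting on: a better method is available at little cost, and both inclusion rules admit subjects whom one reading of the named method would delete.

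**What to change.** Replace repeated measures ANOVA with an MMRM on change from week 0, specified as follows:

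- **Fixed effects:** treatment, visit, treatment-by-visit, week-0 value, week-0 value-by-visit, and the planned stratification variables (BMI, A1C, diabetes treatment).
- **Covariance:** unstructured, with heterogeneous Toeplitz pre-specified as the fallback if the fit does not converge.
- **Estimation:** restricted maximum likelihood with Kenward-Roger degrees of freedom.
- **Data:** all available post-baseline visits of every subject in the analysis set.
- **Reporting:** the treatment difference with its 95% CI at each visit, stating which intervals come from the MMRM and which from the ANCOVA.

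Define the baseline covariate as the week-0 value, since a parallel design has only one treatment period. Reconcile the week-12 and week-8 inclusion rules, because the MMRM does not settle who is analysed.

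The cost is SAP wording and routine programming, with no new data. The small downside is 5 × 6 / 2 = 15 covariance parameters with about 42 subjects, which is why the fallback is needed.

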This is a randomized, double-blind, placebo-controlled parallel design study in which 42 subjects will be randomized (1:1) to treatment with canagliflozin 300mg or placebo once daily for 18 weeks. The study will include 7 outpatient visits which will take place in the Harvard Catalyst Clinical Research Center at BIDMC. The funding source for this study is Janssen Scientific Affairs, LLC; Janssen Scientific Affairs, LLC is also providing canagliflozin for this study.

Our primary endpoint is change in body weight. Secondary endpoints are change in resting metabolic rate measured using indirect calorimetry, change in body composition using DXA scans changes in serum markers of metabolism and inflammation, and change in hunger and satiety using visual analog scales. We will also analyze change in caloric intake using food logs.

Study procedures include a screening visit, an enrollment visit (study week 0), follow-up visits at study weeks 2, 4, 8, and 12, and a final visit at study week 18.

Screening visit: Screening procedures will occur after an overnight fast and will include a full medical history: history of diabetes care and blood sugar control; review of body weight history; review of current medications; a physical exam including height, weight, blood pressure and heart rate; a blood test to measure CBC, electrolytes, kidney function, liver function, thyroid function, cholesterol levels, hemoglobin A1C, and markers of metabolism and inflammation. We will also collect a urine sample for measurement of glucose andcreatinine. We will also measure urine glucose and creatinine levels.

Women of childbearing age will have a urine pregnancy test unless they are over age 50 and have not had a menstrual period in more than 2 years, or have had a surgical procedure which makes it impossible to become pregnant (hysterectomy). If the pregnancy test is positive, the subject will not be allowed to enroll in the study.

Enrollment visit (Study Week 0): The enrollment visit will occur after an overnight fast and will include measurement of vital signs, body composition, and resting metabolic rate. We will also distribute blood sugar logs, visual analog scales, and food logs, and we will do a 24-hour food recall assessment.

Vital signs: For all visits, vital signs will include weight (with the subject wearing a hospital gown), blood pressure lying down and standing, heart rate lying down and standing, and waist circumference.

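### Does the resting metabolic rate (RMR) analysis need adjustment for the weight lost on treatment before it can answer the trial's question?

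*Combined protocol and SAP*

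**What the plan says.** RMR is a secondary endpoint (section B3.A). Section B3.B, Data analysis, gives it two analyses. The first is by visit: "We will use repeated measures analysis of variance to assess changes in body weight and resting metabolic rate at each study visit/timepoint". The second is the ANCOVA used for all secondary endpoints, described as "Treatment group will be the fixed effect and corresponding baseline values at the start of each treatment period will be the covariates". In a parallel-group trial the baseline value is the week 0 value. The stratification factors (BMI, A1C, type of diabetes treatment) are also baseline characteristics. Body composition is handled as an outcome of its own: "We will also analyze change in body composition between baseline and end of study".

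The question behind the RMR endpoint is in section B2: "The mechanisms of weight loss with canagliflozin are not completely understood", and "Specifically, it is not known whether canagliflozin changes resting metabolic rate (RMR". The same section says that knowing the size and duration of changes in energy expenditure "may inform recommendations about lifestyle modification, including a reduced calorie diet and physical activity".

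On data collection (section B3.A): "The enrollment visit will occur after an overnight fast and will include measurement of vital signs, body composition, and resting metabolic rate". The week 18 visit repeats those procedures. RMR and weight are also measured at weeks 2, 4, 8 and 12.

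**The concern.** A lighter body tends to burn less at rest. The trial expects the canagliflozin arm to be about 3 kg lighter than placebo when RMR is compared, yet no post-baseline measurement of weight, fat-free mass or fat mass enters the RMR model. A fall in RMR could then come from lost mass alone, or from lost mass plus a direct drug effect. A null result could mean no direct effect, or a direct rise cancelled by lost mass. Only a rise despite weight loss would be clear in direction.

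The title speaks of mechanisms, and DXA and RMR are both measured at weeks 0 and 18. A reader may therefore expect a model that relates the change in RMR to the change in mass. At stake would be the mechanistic reading of one secondary endpoint. The primary endpoint is not touched.

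**Working it through.** **The question and the estimand.** Section B2 asks whether the drug changes RMR, and wants the size and duration of the change for advice on diet and activity. Both concern RMR as it is on treatment, lost mass included. The planned contrast estimates that total effect and is protected by randomisation. Using only baseline covariates is the normal choice for such a comparison. No section defines a mass-independent effect as an objective.

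**The plan's own figure.** Inputs from section B3.B: difference 3 kg, SD 3.3, two-sided 0.05, 42 completers, so 21 per arm. SE = 3.3 × √(2/21) = 1.018; 3/1.018 = 2.95. The t-test on 40 degrees of freedom gives power 82%, against the stated 80%, so the figure reproduces. The documents give no power or SD for RMR.

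**Assumptions (not in the documents).** RMR slope 10 to 25 kcal/day per kg; residual SD of RMR change, apart from mass, 100 kcal/day (range 80 to 150). The 3 kg is a 12-week figure, applied here at week 18.

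**How far lost mass could move the planned contrast.**
- Shift: 3 × 10 = 30 to 3 × 25 = 75 kcal/day.
- The planned model does not adjust for mass change, so its SD includes that variation: √(100² + (10 × 3.3)²) = 105 and √(100² + (25 × 3.3)²) = 130.
- SE: 105.3 × √(2/21) = 32.5 and 129.6 × √(2/21) = 40.0.
- Shift in SE units: 30/32.5 = 0.9 and 75/40.0 = 1.9. Leaving the mass variation out would give an SE of 31 and overstate the shift as 1.0 to 2.4.
- With no direct effect, simulation gives a significant fall in about 14% to 44% of trials. Each would be a true finding about total RMR.

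**What a mass-adjusted model would add.** Simulated model: treatment, baseline RMR, change in fat-free mass and change in fat mass; 37 degrees of freedom; 25% of mass change fat-free with 0.7 kg scatter; one slope for both tissues.
- SE about 35; 95% half-width 2.026 × 35.2 = 71 kcal/day.
- With a direct rise that exactly offsets the mass effect, the planned estimate averages about 0 and the adjusted one recovers the rise:

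| Residual SD (kcal/day) | Power, direct rise 30 | Power, direct rise 75 |
|---|---|---|
| 80 | 18% | 74% |
| 100 | 13% | 54% |
| 150 | 8% | 29% |

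- Mass change occurs after randomisation, so a common cause of mass change and RMR biases the adjusted estimate. A factor correlated 0.5 with weight change and worth 30 kcal/day per SD gives 30 × 0.5/3.3 × 3 = 13.6 kcal/day, in either direction.
- A fluid loss of 0.5 to 1.0 kg on canagliflozin, read by DXA as fat-free mass with no effect on RMR, biases the estimate upward by about 5 to 26 kcal/day. That is towards a false direct rise.

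**What the plan already offers.** If the 3 kg accrues linearly to week 12, the mass difference is 0.5 kg at week 2 and 1.0 kg at week 4. The shift is then 5 to 12.5 and 10 to 25 kcal/day: at most 0.4 and 0.8 of an SE of 31, which is a floor for the planned SE. Faster early loss would enlarge these. The early contrasts therefore carry less mass effect, and weight and body composition are reported alongside.

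**The case for a change.** The best case for adding the analysis is that it is nearly free. The data are collected anyway, one paragraph would pre-specify it, and no planned estimate or sample size would change. Specifying it in advance would avoid choosing a mass covariate after seeing the data. The precision cost is small: the adjusted SE of 35 compares with a planned SE of 33 at slope 10 and 40 at slope 25. Under ideal assumptions it centres on the direct effect, where the planned estimate centres on the total. The early visits also cannot show a direct effect that appears late.

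All of that stands, as does the observation that no post-baseline covariate enters the RMR model. It makes a case for an optional extra and shows no fault in the plan. With a half-width of 71 kcal/day, an adjusted null would generally not separate 0 from a rise of 30, and often not from 75. The possible biases are of the same order as the smaller signal: 26/75 = 34% of the shift at slope 25 for a 1 kg fluid artefact, and a similar share at slope 10 (about 10/30). One ambiguity could be exchanged for another. The plan does not preclude the analysis, so it can still be run and labelled exploratory.

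**Conclusion.** The concern does not hold. The planned RMR comparison is valid, answers the question section B2 poses, and estimates the quantity that matters for its stated use. Its ambiguity about mechanism is real but limited: it affects the interpretation of a null result or a fall in one secondary endpoint, not the correctness of any estimate. Under the assumed slopes, lost mass could account for 30 to 75 kcal/day, about 0.9 to 1.9 SE of the planned contrast. The adjusted alternative would detect an offsetting direct effect of that size with only 13% to 54% power at SD 100, and without the protection of randomisation. Whether to add it is a matter of preference on which reasonable statisticians differ.

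The RMR figures rest on the assumed slopes, residual SD, tissue split, accrual shape and bias scenarios. Only the 3 kg, the SD of 3.3 and the 21 per arm come from the documents. The conclusion does not depend on the assumed values, because it follows from the match between the stated question and the planned estimand.
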